7.3. Recording of Adverse Events

Once the subject has signed the informed consent, information on all adverse events should be recorded immediately in the source document.

Any adverse event which occurs during the reporting period which is related to the device or meets the definition of serious should be documented via a Serious Adverse Event Form. AE's can be documented via an Adverse Event Form. All complications will be treated with appropriate medical care.

Any device-related Adverse Event will be documented in detail as indicated on the CRF. The following information is required:

- Onset date of the AE
- Description of the event (All clearly related signs, symptoms, and abnormal diagnostic procedure results should be recorded in the source document, though they should be grouped under one diagnosis on the CRF)
- Seriousness of the event
- Intensity of the event (mild, moderate or severe; see definitions below)
- Relationship of the AE to the investigational device (see definitions below)
- Any action taken to resolve the AE
- Outcome of the AE (recovered, recovered with sequela, or on going)
- Stop date of the AE if not indicated as on going

Intensity

The investigator is to classify the intensity of an AE according to the following definitions:

Mild: Transient symptoms, no interference with the subject's daily activities.

Moderate: Marked symptoms, moderate interference with the subject's daily activities.

Severe: The subject is unable to perform usual activity.

Relationship

The investigator is to classify the investigational device relationship of an AE according to the following definitions:

Not related: The time between implantation of the investigational device and occurrence or worsening of the AE rules out a casual relationship, and/or another cause is confirmed and no indication of involvement of the investigational device in the occurrence/worsening of the AE exists.

Unlikely: The time between implantation of investigational device and occurrence or worsening of the AE makes a casual relationship unlikely, and/or the known effects of the investigational device provide no indication of involvement in occurrence/worsening of the AE, and another cause adequately explaining the AE is known, and/or regarding the

occurrence/worsening of the AE a plausible causal chain may be deduced from the known effects of the investigational device, but another cause is much more probable, and/or another cause is confirmed and involvement of the investigational device in the occurrence/worsening of the AE is unlikely.

Possibly: An AE that might be due to the use of the device. An alternative explanation (e.g. concomitant drug(s), concomitant disease(s)) is inconclusive. The relationship in time is reasonable; therefore the casual relationship cannot be excluded.

Probably: An AE that might be due to the use of the device. The relationship in time is suggestive (e.g. confirmed by dechallenge). An alternative explanation is less likely (e.g. concomitant drug(s), concomitant disease(s)).

Definitely: An AE that is listed as a possible adverse reaction and cannot be reasonably explained by an alternative explanation, e.g. concomitant drug(s), concomitant disease(s). The relationship in time is very suggestive (e.g. it is confirmed by dechallenge and rechallenge)

The clinical course of each device-related event should be followed until resolution, stabilisation, or until it has been determined that the study treatment or participation is not the cause.

7.4. Reporting of Serious Adverse Events and Adverse Device Events

7.4.1 Study Sponsor Notification by Investigator

Any serious adverse event or adverse device event must be reported by the Investigator to the Safety Responsible at Stryker by telephone within 24 hours or at the latest on the following working day.

A Serious Adverse Event Form must be completed by the investigator and faxed to Stryker within 3 working days. The reporting language is English. The investigator will keep a copy of this SAE form on file at the study site. Serious Adverse Events should be reported by phone to:

[name], CRA

[contact]

[contact]

[contact]

Email: [contact]

7.4.2 METC Notification by Investigator

Reports of serious adverse device effects - including follow-up information - must be submitted within 48 hours to Stryker and the accredited METC that approved the protocol, according to the requirements of that METC. Copies of each report and documentation of METC notification and receipt will be kept in the Investigator Site File and also in the study Master File.

7.5. Period of Observation

For the purpose of the study, the period of observation for collection of adverse events extends from the time the subject gives informed consent until the date of last study visit or last contact with the subject.

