4.3.1 Specific Criteria for Withdrawal /Termination

In the event that a subject is discontinued from the study for any reason, the site will complete a Study Termination form. Subjects may be withdrawn for the following reasons:

- Patient failure – defined by the requirements at the two- year follow-up interval see section 6.1.3.
- Any Serious Adverse Event that effects the outcome of the study
- Any Serious Adverse Event related to the test device
- Revision/Removal of study device
- Patient withdrawal (patients own request)
- Lost to Follow-Up

- If, in the Investigator's opinion, continuation in the study would be detrimental to the subject's well being (a written explanation is required)
- Completion of study and final evaluation
- Death of the subject

If the patient fails to return for their follow-up appointments, every effort should be made to contact the subject to assess their health status. If after attempting to contact the patient through 3 documented phone calls and a certified (i.e., return-receipt) letter, the patient still does not respond, the patient will be considered as "lost to follow-up". A Study Termination Form will be completed after notifying Stryker of the patient's status.

In the event that the subject is discontinued by the investigative site prior to the final study evaluation, the subject is notified that they are no longer in the study and a Study Termination form will be completed.

Following discontinuation, the subject will be seen regularly as considered clinically appropriate. If the discontinuation was caused by an adverse event the subject will be seen regularly until the symptoms have disappeared or are under control, or until feasible treatment has been undertaken. Refusal to participate or early withdrawal from this investigation will not affect the quality or availability of the subject's medical care.

Subjects withdrawn from the study will keep their subject number. New subjects must always be assigned a new subject number. In the event that the subject withdraws from this investigation, the information that has already been collected will be included in the database and in the final analyses. The subject's medical records will also be available for monitoring, auditing and inspection purposes.

After withdrawal subjects will not be replaced to the study.

5. Subject Enrolment

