Surgical approach		
Soft tissue released		
Navigation		
Deviation from site-specific surgical procedure		
Bone removed	Femur Tibia Slope	
Tantalum balls (ø 1.0 mm)	Position in the tibia bone	
Time	Skin to skin Tourniquet	
Implant details	Sizes of components Product labels	
Intra-operative complications		

Assessment at on week postoperative

Clinical evaluation	Concomitant therapy	Pain medication
	Systemic prophylactic therapy	Antibiotic Anticoagulant
	Rehabilitation/mobilization	Site specific procedure Discharged
Radiographic assessment	Anterior/posterior Lateral Radiostereometric analysis	
Early post-op complications		

Follow-up assessment at 6 weeks, 3 months, 6 months, 1 year, 2 years and 5 years

Clinical evaluation	Patient status	
	Concomitant therapy	Pain medication
	AKSS*	
	Patient questionnaires	SF-36 EQ-5D
Radiographic assessment	Anterior/posterior Lateral Radiostereometric analysis	

Complications		
---------------	--	--

Termination

Date of evaluation		
Study completion	Reason for early termination	
Position of study device at last contact to patient		
Problems at last contact		

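### Adverse event and revision collection can stop when a patient is withdrawn for a device event or two-year failure, so later events may go unrecorded and by-arm safety results may be biased

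*Combined protocol and SAP*

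**What the plan says.** Section 7.5 sets the adverse event window: it "extends from the time the subject gives informed consent until the date of last study visit or last contact with the subject". It does not define what counts as the last contact.

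Section 4.3.1 opens its list of exits with "Subjects may be withdrawn for the following reasons". Three of the reasons are outcomes: "Any Serious Adverse Event related to the test device", "Revision/Removal of study device" and "Patient failure – defined by the requirements at the two- year follow-up interval see section 6.1.3". Section 6.1.3 makes two-year failure broad. A Knee Score below 80, osteolysis, excess migration, or a revision that is pending or already done is each enough.

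When the site discontinues a patient early, "the subject is notified that they are no longer in the study" and a termination form is completed. The termination table in section 6 includes the item "Position of study device at last contact to patient". Section 4.3.1 then adds: "Following discontinuation, the subject will be seen regularly as considered clinically appropriate". If an adverse event caused the exit, these visits go on until symptoms settle or treatment has been given. Section 7.3 also has the course of each device-related event followed until it resolves or is stable. Where the patient withdraws, section 4.3.1 brings into the analysis the data gathered up to then and is silent on anything later.

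Section 6 states five years of follow-up after implantation for each patient. Section 6.1.2 makes absence of revision a durability endpoint, and section 9.1 promises a 95% confidence interval for survival.

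**The concern.** The end of observation is tied to participation, and participation may be ended by the outcomes that safety and durability reporting are meant to count. A patient who leaves at two years with a low Knee Score, osteolysis or a pending revision has not yet been revised. If the revision takes place in year 3, no stated rule brings it into the database. The possible loss therefore goes beyond complications after a revision and includes the first revision itself.

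If the two inserts fail at different rates, the arm with more failures can lose more observation, and the loss falls on the patients most likely to have further events. Section 9 describes chi-square and Fisher tests for categorical outcomes and does not say how unequal observation time is handled.

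**Working it through.** **The plan's own figures.** The plan gives no figure for adverse event exposure, failure or withdrawal. Its only power figure is for wear (section 3.2): 27 per group, difference 0.1 mm, SD 0.1, two-sided alpha 0.05. The noncentrality is 0.1 / (0.1 × √(2/27)) = 3.67, and the exact t-test power on 52 degrees of freedom is 0.950, so the stated 95% reproduces. This point does not affect that calculation.

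**Reading the rules together.**

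| Situation | What the documents require |
|---|---|
| The event that triggers the exit | Recorded (7.3) and followed (4.3.1, 7.3) |
| Clinic visits after discontinuation | Take place as clinically needed (4.3.1); no data capture stated |
| A new SAE or first revision after discontinuation | No rule; depends on whether a later clinic visit counts as the last contact (7.5) |
| Follow-up length | Five years for each patient (6) |

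**Person-time.** Inputs from the documents are 50 patients per arm (3.2) and 5 years (6). The failure share *f* is assumed. If every failure leaves at year 2, each loses 3 years, so person-years per arm = 50 × (5 − 3*f*). If half leave, *f* is replaced by *f*/2.

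| Assumed shares | All failures leave | Ratio | Half leave | Ratio |
|---|---|---|---|---|
| 5% v 10% | 242.5 v 235.0 | 0.97 | 246.25 v 242.5 | 0.98 |
| 10% v 20% | 235.0 v 220.0 | 0.94 | 242.5 v 235.0 | 0.97 |
| 10% v 30% | 235.0 v 205.0 | 0.87 | 242.5 v 227.5 | 0.94 |

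If failures stay under adverse event collection, both arms have 250 person-years, ignoring other losses.

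**Event counts.** Assume failure shares of 10% v 20%, 0.05 events a year without or before failure, and 0.30 a year after failure at year 2.

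- Over five years: 50 × (0.9 × 0.25 + 0.1 × (0.10 + 0.90)) = 16.25, against 50 × (0.8 × 0.25 + 0.2 × (0.10 + 0.90)) = 20.0. The ratio is 1.23.
- Counted if all failures leave: 50 × (0.225 + 0.1 × 0.10) = 11.75, against 50 × (0.200 + 0.2 × 0.10) = 11.0. The ratio is 0.94.
- Counted if half leave: 16.25 − 2.25 = 14.0, against 20.0 − 4.5 = 15.5. The ratio is 1.11.
- With 0.10 a year after failure, the five-year counts are 13.25 and 14.0 (ratio 1.06). The counted ratio if all leave is again 0.94.

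Dividing by observed time does not repair this. With all failures leaving, 11.75/235 and 11.0/220 are both 0.05 a year, a ratio of 1.00 where full collection gives 1.23. The missing events have to be collected.

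**Missed five-year visit.** If, as an assumption, 20% of an arm attend year 2, miss year 5 and cannot be reached, 10 × 3 = 30 of 250 person-years (12%) are unobserved. This is an upper bound for that share of non-attenders, because section 4.3.1 requires attempts to reach them. It is the same in both arms, so it costs information without itself creating a difference between arms.

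**The case against.** The strongest reply is that the gap is one of wording. Withdrawal is permitted and not required, so an investigator may keep a revised or failed patient in follow-up. The event that ends participation is recorded and followed, and some later complications would belong to its course. The schedule in section 6 lists adverse events, including revision, as collected at any time. A clinic visit after discontinuation might count as a contact under section 7.5. Non-attenders must be pursued by three logged calls and a certified letter. A chi-square comparison counts patients in categories, so a second event of the same kind in a patient already counted changes nothing.

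Most of this stands, and it limits the claim. A reader might infer that the arm with more failures is necessarily observed for less time and that its later harms are necessarily lost. The documents do not support that: withdrawal is discretionary and the last contact is undefined. Nor do they show that bias must run towards no difference; in the illustrations above it ranges from attenuation to reversal. They also do not place late failures in years 2 to 5. Section 1.1 speaks of failure after more than two years with no upper limit, and section 8.2 gives no years for late loosening. Starting collection at consent is not a material fault, since it applies to both arms and pre-operative events can be listed separately.

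The reply does not close the gap for a patient withdrawn without an earlier SAE or revision, such as one with a Knee Score below 80, or for a new type of event. No rule says when the discretion to withdraw is used, and no rule requires recording afterwards.

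**Conclusion.** The concern holds as a risk created by sections 7.5 and 4.3.1 read together. The stated rules let the end of adverse event and revision collection depend on outcome, and they leave it open whether a first revision after a two-year failure withdrawal is ever counted. That affects the durability endpoint and the survival interval as well as the safety tables.

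The person-time effect is modest: about 3–13% less in the worse arm if all failures leave at year 2, and about 2–6% less if half leave. The effect on event counts can be larger, because the lost time belongs to patients who have already failed. All of these sizes rest on assumed failure shares and event rates, and the actual effect depends on how often withdrawal is used. The wear sample size is unaffected. The plan should be changed, because the ambiguity is cheap to remove now and the missing events would be hard to recover later.

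**What to change.** Reconcile sections 7.5, 4.3.1 and 6, without changing the clinical grounds for discontinuation:

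- In 7.5, state that for every implanted patient adverse event, SAE and revision data are collected to five years after surgery, whatever the visit attendance or discontinuation status. Collection ends earlier only at death or withdrawal of consent to data collection. Define the last contact.
- In 4.3.1, amend the notice to the patient so that it says study visits end but safety and revision data continue to be recorded. Changing 7.5 alone would leave the two sections in conflict.
- Record new events at the clinic contacts and contact attempts that 4.3.1 already foresees. For non-attenders, add one check of the hospital record at the five-year date.
- In section 9, report revisions by time to event and SAEs per patient-year by arm, with reasons for discontinuation by arm.

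The cost is protocol wording, some additional forms and one record check per non-attender, with no added study visits or imaging. The downside is a small amount of site work, and hospital record checks will miss events treated elsewhere.

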7.6. Medical Monitoring

It is the responsibility of the Investigator to oversee the safety of the study at his/her site. This safety monitoring will include careful assessment and appropriate reporting of adverse events as noted above.

8. Risk / Benefit Assessment

8.1. Risk Category

There is minimal risk associated with participating in this study over and above that of the primary knee arthroplasty procedure.

8.2. Potential Risk

The study involves the routine assessment of a knee arthroplasty procedure. The device under study has been cleared for marketing and has the CE mark. It will be used according to its labelling. Assessment involves questionnaires, patient and physician assessments, and RSA-radiographs. The effective radiation dose per RSA-radiograph is 3 μ Sv (Teeuwisse *et al.*, 1998). The additional annual radiation dose is negligible if the natural annual exposure of 2 mSv is considered and will do the patient no harm (Blake *et al.*, 1996). The International Commission on Radiological Protection categorizes the corresponding level of risk qualitative due to radiation as 'trivial' with a quantitative risk of about one in a million or less. The required level of benefit should be related to 'only increase knowledge'. (http://ec.europa.eu/energy/nuclear/radioprotection/publication/099_en.htm)

The information collected will be kept confidential.

Serious complications may be associated with any total joint replacement surgery. These complications include, but are not limited to: infection, genitourinary disorders, gastrointestinal disorders, vascular disorders, including thrombus, bronchopulmonary disorders, including emboli, myocardial infarction and death.

With all implanted devices, asymptomatic, localized progressive bone resorption (osteolysis) may occur around the prosthetic components as a consequence of foreign-body reaction to the particulate matter of metal or polyethylene (X3, UHMWPE). Particulate is generated by interaction between components as well as adhesion, abrasion, and fatigue. Secondly, particulates can also be generated by third body wear. Osteolysis can lead to future complications, including loosening, necessitating the removal and replacement of prosthetic components.

Early and late loosening of total knee components can occur. Early biomechanical loosening may result from inadequate initial fixation, latent infection, premature loading of the prosthesis or trauma. Late loosening may result from trauma, infection, biological complications including osteolysis or mechanical problems, with the subsequent possibility of bone erosion and/or pain.

Peripheral neuropathies, circulatory compromise and heterotopic bone formation may occur.

Intraoperative fissure, fracture, or perforation of the femur or tibia can occur due to impaction of the component into the prepared femur or tibia. Postoperative femoral or tibial fracture can occur due to trauma, the presence of defects, or poor bone stock.

Metal sensitivity reactions have been reported following joint replacement.

Adverse events may necessitate reoperation, revision and in rare cases arthrodesis of the involved joint, girdlestone or amputation of the limb.

8.3. Protection Against Risks

Patients will be treated in the best medical judgment of the investigator, regardless of the study protocol. If an investigator must deviate from the written protocol to protect the health or well being of the patient, this deviation will be promptly reported to the Ethics Committee and a protocol deviation form shall be completed.

8.4. Potential benefits to the Subject

In addition to the benefits from the primary knee arthroplasty procedure e.g. reduced pain, improved range of motion, there is no guarantee that patients will personally benefit from inclusion in this study. Patients may undergo more thorough screening and follow-up than non-study patients and may benefit from this increased surveillance. This study seeks to provide clinicians information about this system/device by comparing this treatment/device to published results for other treatments/devices. Information gathered in this study may benefit others undergoing this procedure in the future.

9. Statistical Plan

9.1. Statistical Methods

Continuous outcome variables and their differences will be analyzed with parametrical statistical techniques, such as t-tests, unless the normality assumption does not seem reasonable for the data, in which case non-parametric techniques will be considered e.g. Wilcoxon/Mann-Whitney tests.

Categorical outcome variables will be analyzed with chi-square tests and/or Fisher's exact tests (depending on the expected values in the categories). For the relevant parameters (subsidence, survival, pain and function) also the 95 percent confidence intervals will be calculated.

The effect of parameters such as age, sex and operators will be evaluated using multiple variate analysis. All data will be analyzed by blinded researchers.

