1.3. Beads

To evaluate the motion of the polyethylene bearing and micromotion of the prosthesis, at least three well-scattered tantalum balls (∅ 1.0 mm) have to be inserted into the tibia and femoral bone. To this end a special designed Ta-marker insertion device will be used according to instructions of the manufacturer (Halifax Biomedical, NS, Canada). The beads are not part of the Knee system itself. The bead inserter

device will be loaned to the hospital by Stryker for the duration of the clinical study (covered in study contract).

2. Objectives of the Clinical Investigation

- The primary objective is the assessment of the in vivo wear of the two randomized polyethylene inlay types N2Vac and X3 by means of Roentgen Stereophotogrammetry. It is expected that the X3 group will show significantly less wear after 5 years compared to the conventional N2Vac polyethylene group.
- The secondary objective is the assessment of prosthetic migration results after two years of the Triathlon CS Peri-Apatite coated tibial and femoral components by means of Roentgen Stereophotogrammetry. It is expected that due to the superior wear qualities of X3 polyethylene this group will show significantly less migration of the prosthesis' components after two-years compared to the components in the N2Vac group.
- The third objective will be the prediction of the long-term survival of the Triathlon CS Peri-Apatite coated tibial and femoral components based on the two-year migration patterns combined with clinical factors and radiographic aspects. In order to identify other clinical parameters besides wear influencing the fixation of the prosthesis components, clinical scores and radiographic aspects will be correlated with the RSA outcome. Subsequently, a long-term prediction can be for the Triathlon CS Peri-Apatite coated tibial and femoral components.

3. Design of the Clinical Investigation

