3.2. Number of Subjects

RSA is able to measure wear with high accuracy. Previous RSA wear studies show that the expected wear rate is 0.13 ± 0.08 mm a year (Short et al., 2005; Kellett et al., 2004). A clinical relevant difference to detect differences in wear would be a standard deviation of 0.1 mm a year.

Group sample sizes of 27 patients in each group would achieve 95% power to detect a difference of -0.1 mm wear between the null hypothesis that both group means are 0 and the alternative hypothesis that the mean of group 2 is 0.1 with estimated group standard deviations of 0.1 and with a significance level (alpha) of 0.05 using a two-sided two-sample t-test.

However, in order to also achieve the third objective of this protocol whereby clinical parameters will be correlated with RSA results, more patients are needed to obtain stronger correlations with the important

clinical outcome parameters. Taking the latter in account and to compensate for possible lost to follow up, 50 patients will be recruited per study group.

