9.2. Missing Data

No imputation of missing data will be made. If any questionnaire (e.g., AKSS) has a missing item, the total score for that scale will be considered missing.

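### Section 9.1 does not name the pre-operative score as covariate for the clinical scores, omits wear from the 95% CI list, and gives earlier wear readings no role when the 5-year film is missing

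*Combined protocol and SAP*

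**What the plan says.** Section 9.1 sets the method for every continuous outcome in one sentence: "Continuous outcome variables and their differences will be analyzed with parametrical statistical techniques, such as t-tests", or rank tests if normality looks unreasonable. A separate sentence covers other variables: "The effect of parameters such as age, sex and operators will be evaluated using multiple variate analysis". It is tied to no outcome and does not mention the pre-operative score. On intervals it says "For the relevant parameters (subsidence, survival, pain and function) also the 95 percent confidence intervals will be calculated".

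The study summary names wear as the primary endpoint. Section 2 fixes the time point: "It is expected that the X3 group will show significantly less wear after 5 years". Section 3.2 sizes the trial for a two-sided two-sample t-test. Section 6.3 schedules RSA films at discharge (the reference film), 6 weeks, 3, 6, 12 and 24 months, and 5 years.

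Section 6 collects KSS, SF-36, EQ-5D and LEAS before surgery, and section 6.1.1 defines pain relief and function as a rise in the KSS components. Section 9.2 states "No imputation of missing data will be made". For withdrawn patients, section 4.3.1 says "the information that has already been collected will be included in the database and in the final analyses".

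**The concern.** There are three gaps, and no other section closes them.

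1. **Clinical scores.** Section 6.1.1 and the reference to differences in 9.1 point to change scores, at least for KSS. A change score uses the baseline by plain subtraction. That is less efficient than adjustment unless the regression slope of follow-up on baseline happens to be 1.
2. **Interval for wear.** Outcomes other than the primary one are promised a confidence interval. The primary one is promised only a test. Subsidence does not stand in for wear, because section 6.3 lists the two separately and defines wear as femoral movement relative to the tibia.
3. **Missing 5-year films.** Three years pass between the last two films, and section 3.2 itself allows for loss to follow-up. A test on 5-year values without imputation drops every patient who lacks that film, even if five earlier post-discharge readings exist.

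At stake are some precision on the clinical scores, an effect estimate that a reader can interpret for the primary endpoint, and a check on how far the primary result depends on who came back at 5 years.

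**Working it through.** **The plan's own figure.** Inputs from section 3.2: difference 0.1, SD 0.1, two-sided alpha 0.05, two-sample t-test. Noncentral-t power is 94.2% at 26 per group and 95.0% at 27, so the stated 27 reproduces. On the same inputs, power is 99.9% at 50 per arm, 99.3% at 40 (20% lost) and 98.5% at 35 (30% lost). It falls to 95% only when 1 − 27/50 = 46% of each arm is lost.

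**Clinical scores.** Set the follow-up variance to 1, the baseline SD to k and the pre/post correlation to r. The documents give neither k nor r, so both are assumed. Variance per patient:
- follow-up score alone: 1
- change score: 1 + k² − 2rk
- ANCOVA: 1 − r²

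| r | ANCOVA | Change, k = 1 | ANCOVA below change | Change, k = 0.7 | ANCOVA below change | ANCOVA below follow-up alone |
|---|---|---|---|---|---|---|
| 0.3 | 0.91 | 1.40 | 35% | 1.07 | 15% | 9% |
| 0.5 | 0.75 | 1.00 | 25% | 0.79 | 5% | 25% |
| 0.7 | 0.51 | 0.60 | 15% | 0.51 | 0% | 49% |

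A k below 1 is plausible for KSS, because eligibility requires a pre-operative score under 70 and so narrows the baseline range. In large samples ANCOVA is never worse than either alternative.

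**Interval for wear.** Half-width = t(0.975, 2n − 2) × SD × √(2/n). With SD 0.1 this is 1.984 × 0.1 × 0.200 = 0.040 at 50 per arm, and 0.055 at 27. The unit is that of section 3.2, which speaks of "A clinical relevant difference to detect differences in wear would be a standard deviation of 0.1 mm a year" and then of power "to detect a difference of -0.1 mm wear between the null hypothesis" with no period.

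**What earlier films add to precision.** If a share m of 5-year films is missing and earlier wear correlates r with 5-year wear (both assumed), a likelihood model has an effective number per arm of 1 / [(1 − r²)/(n(1 − m)) + r²/n]. For n = 50, m = 0.3, r = 0.5 this is 1 / (0.75/35 + 0.25/50) = 37.8, against 35 complete cases. Over r = 0.3 to 0.7 the range is 36.0 to 41.0. With power already at 98.5% for 35 per arm, this gain matters little.

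**Bias from missing films.** If dropout does not depend on wear, the t-test on observed 5-year values is unbiased. If it does, the sign follows from who is lost, with N2Vac expected to wear more:
- High-wear patients lost from N2Vac only, or low-wear patients lost from X3 only: the difference shrinks.
- Low-wear patients lost from N2Vac only, or high-wear patients lost from X3 only: the difference grows.
- The same dependence in both arms: the difference shrinks, given the equal SDs that section 3.2 assumes.

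A simulation shows the pattern. Everything in it beyond section 3.2's rates and SD and the RSA accuracy in section 1.1 is assumed: wear rates of 0.13 and 0.03 mm a year, SD 0.1, linear wear, RSA error SD 0.25/1.96 = 0.128 mm, 20% base dropout after year 2, and logistic dependence on observed 2-year wear with slope 3 or 7 per mm. The error in the 5-year difference is about −5% or −17% with both arms affected. It is about −15% or −37% if high-wear N2Vac patients are lost, and +10% or +20% if low-wear N2Vac patients are lost instead. If section 3.2 means 0.1 mm in total, no error from losing high-wear patients at 10 to 30% base dropout exceeds 8% in either direction. These figures show that the sign is open. They do not estimate this trial's bias.

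**The case against.** The strongest reply is that 9.1 is open-ended rather than wrong. Its wording permits ANCOVA and mixed models. Its t-test sentence covers wear, because wear is continuous, and section 3.2 makes that specific. This stands: the primary method is not absent, and the clinical-score gap is one of naming. But permission is not pre-specification, and nothing in the reply supplies the interval for wear.

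A reader might infer more in three ways, and the documents do not support any of them.

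- **That the primary result will be biased, in a known direction.** No section links dropout to wear. The RSA analysis is done by an outside CRO, patients and data analysers are blinded, and wear is not a failure criterion in section 6.1.3. The direction is not fixed either. Section 1.1 ties more wear to younger, more active patients, so losses through death or age could fall on low-wear patients.
- **That a 5-year t-test contradicts section 4.3.1.** It does not. Data from withdrawn patients can enter the final analyses through the earlier visits.
- **That a repeated-measures model should replace the t-test as primary.** Power is ample without it. The model is unbiased only when dropout depends on wear already observed, so a simulation built on that mechanism favours it by construction. If 3.2 means 0.1 mm in total and RSA error adds to its SD, the model gains no power and, with covariance separate by arm, can lose about 3 points (83.3% to 80.3% at 10% dropout).

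**Conclusion.** The point holds as three omissions from section 9.1, and it should be fixed. Adding the wear interval needs no assumption. Naming the pre-operative score as covariate is a free improvement whose size rests on unknown correlations and SDs: 0 to 35% less variance than change scores, and 9 to 49% less than follow-up scores alone, over the range shown. It is secondary in importance, because the comparative hypotheses in section 2 concern wear and migration.

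The case for using the earlier wear readings is robustness to missing 5-year films, not power. The t-test is biased only if dropout depends on wear. Dependence alike in both arms pulls the difference toward zero when the SDs are equal. Dependence in one arm can push it either way. A likelihood model corrects this only if the dependence runs through observed wear, so it does not fully cover dropout driven by knee score, osteolysis or migration. That supports a sensitivity analysis and leaves the primary test as it is.

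**What to change.** In section 9.1:

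(a) Compare KSS, SF-36, EQ-5D and LEAS between arms by ANCOVA with the pre-operative score as covariate.

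(b) Add the between-arm difference in 5-year wear to the list of parameters reported with a 95% confidence interval.

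(c) Name the two-sample t-test (or rank test) on observed 5-year wear as the primary analysis, as section 3.2 sizes it. Add a likelihood-based repeated-measures model on all post-discharge RSA visits (arm, visit and their interaction) as a sensitivity analysis, with the covariance structure and the fallback for non-convergence fixed in advance. Report missing 5-year films by arm with reasons.

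The cost is a short SAP amendment and a little programming. No new data are needed, and a likelihood model involves no imputation, so section 9.2 stands. Under 9.2 a patient with an incomplete pre-operative scale would drop out of ANCOVA, as already happens with a change score. The model assumes roughly normal wear, so some bias can remain if wear is skewed.
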